### **3.8 Restrictions**

#### **3.8.1 Prohibited and/or restricted treatments**

Once enrolled, subjects may not receive any of the following for the duration of the screening, open-label, double-blind treatment periods:

- Antihyperglycemic medication (other than protocol required medication and/or protocol-allowed open-label rescue medication).
- Treatment with any stable replacement or chronic corticosteroid therapy at the time of screening is permitted. During the trial (beginning with screening), newly initiation of treatment with any systemic corticosteroid therapy that will involve  $\geq 5$  days of therapy is not permitted (inhaled and topical are allowed). The AstraZeneca study physician should be consulted prior to the beginning of therapy for subjects who require systemic corticosteroid treatment.
- In countries where dose adjustment would be required by the local saxagliptin label: if initiation of treatment with any potent cytochrome P450 3A4/5 inhibitor during the trial is required, the AstraZeneca study physician should be consulted prior to beginning therapy with any potent cytochrome P450 3A4/5 inhibitor.

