### **3.9.3 Procedures for discontinuation of a subject from investigational product**

At any time, subjects are free to discontinue IP or withdraw from the study (i.e., IP and assessments – see Section 3.10), without prejudice to further treatment. A subject that decides to discontinue IP will always be asked about the reason(s) and the presence of any AEs. If possible, they will be seen and assessed by an investigator(s). AEs will be followed up (See Section 6.3.2); diary cards and all study medications should be returned by the subject.

Subjects who discontinue the IP and/or study early will have Early treatment discontinuation (ETD) procedures performed as shown in the Study Schedule (refer to Section 4).

Subjects that discontinue IP should continue in the study returning on their next regularly scheduled visits. At their next regularly scheduled visits all protocol specified visits and procedures should be performed with the exception of IP management. Medication for the management of subject's diabetes would be under care and direction of the investigator. The only exception to this requirement is when a subject withdraws consent for all study procedures or loses the ability to consent freely (i.e., is imprisoned or involuntarily incarcerated for the treatment of either a psychiatric or physical illness).

If a subject is withdrawn from study, see Section 3.10.

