**Table 2      Lack of glycaemic control criteria for initiation of rescue medication**

Visit Label	Central Laboratory FPG
Week 6	FPG > 270 mg/dL (15.0 mmol/L)
After Week 6 up to but not including Week 12	FPG > 240 mg/dL (13.3 mmol/L)
From Week 12 up to but not including Week 24	FPG > 200 mg/dL (11.1 mmol/L)

Subjects with a central laboratory FPG value meeting the lack of glycaemic control criterion at a pre-specified visit will be scheduled for a follow-up visit (within 3 - 5 days following receipt of FPG value from central laboratory) to obtain a second central laboratory FPG value and review the subject's glucose meter readings. If the repeat central laboratory FPG value still meets the criterion, the subject must be rescued. Subjects should continue receiving study medication while receiving rescue therapy. Subjects who meet rescue criteria in the double-blind treatment period must first complete the Rescue Visit procedures before receiving open-label rescue medication to ensure that important trial endpoint measurements are collected (See Section 4.3.3). Following completion of the Rescue Visit, rescued subjects will be given open-label rescue medication to be initiated at the lowest starting dose and titrated in accordance with the approved product label in the applicable country at the discretion of the investigator, in addition to their double-blinded study medication. Rescued subjects will then continue in the double-blind treatment period according to their original visit schedule. Following initiation of open-label rescue antidiabetic medication, rescued subjects should be scheduled for titration visits (either on site visits or telephone visits are determined by investigators) to increase their antidiabetic medication dose, as tolerated and in accordance with the approved product label for that country and by their glycaemic response and as per the investigator's judgment. Adjustment of study medication (includes metformin) will not be allowed at any time during the study.

Note: Rescue medication will not be provided by Sponsor in this study.

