3.7	Loss of ability to freely provide consent	Loss of ability to freely provide consent through imprisonment or involuntary incarceration for treatment of either a psychiatric or physical (e.g., infectious disease) illness		
3.8	eGFR	eGFR < 60mL/min/1.73m  for sustained period of time (12 - 16 weeks) Note: Dapagliflozin based on its MOA has been shown to reduce eGFR by up to 10% with initiation of therapy; however, this has in general been reversible and not resulted in renal failure and eGFR values returned to baseline within 12 – 24 weeks of continued therapy.		
3.9	Hepatic function	Initial and repeat laboratory tests meet any of the following criteria: 
 
– ALT and/or AST are >3 x ULN and TB >2 x ULN
 
– ALT and/or AST are >5 x ULN for ≥14 consecutive days, at any time after initial confirmatory results
 
– ALT and/or AST are >8 x ULN
 
		
3.10	DKA	Consider to temporary interrupt dapagliflozin if DKA is suspected. The subject should be promptly evaluated. If DKA is confirmed, dapagliflozin should be discontinued permanently.		
3.11	Hypoglycaemia	Hypoglycaemia events as defined in CSP Section 3.9.2		
4. Concomitant & Other Study Medication Deviations				
4.1	Prohibited medications during the study	a. Randomised subjects who used anti-hyperglycemic therapy (other than protocol required medications) for ≥14 consecutive days during the	5. Randomised subjects who used anti-hyperglycemic therapy (other than protocol required	Partially exclude from PP analysis set (if occurs during double blind)

IPD code	IPD Category	Explanation	PP Relevant IPD	Exclusion level

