		
open-label or double-blind period.
 
b. Randomised subjects newly initiating or changing treatment with systemic glucocorticoids for <math>\geq 5</math> days after enrolment
 
c. Randomized subjects receive potent cytochrome P450 3A4/5 inhibitor for <math>\geq 14</math> consecutive days during the open-label or double-blind period, without consultation between investigator and study physician.
	
medications) for <math>\geq 14</math> consecutive days during the open-label or double-blind period.
 
6. Randomised subjects newly initiating or changing treatment with systemic glucocorticoids for <math>\geq 5</math> days after enrolment
	
Completely exclude from PP analysis set (if occurs during open label)
 
5. Assess relevant deviation for subjects who are randomised. Assess the open-label and double-blind treatment periods together.
 
Exclusion would start from the 14th consecutive day that the medication is taken.
 
6. Assess relevant deviation for subjects who are randomised. Assess the open-label and double-blind treatment periods together. Change includes up or down titration.
 
Exclusion would start from the 5th day that the medication is taken.

4.2	Adjustment of background medication	Randomised subjects who took metformin $< 1500$ mg per day or adjusted from their maximal tolerated dose for $\geq 2$ consecutive weeks after enrolment	7. Randomised subjects who took metformin $< 1500$ mg per day or adjusted from their maximal tolerated dose for $\geq 2$ consecutive weeks after enrolment	
Partially exclude from PP analysis set (if occurs during double blind) Completely exclude from PP analysis set (if occurs during open label).
 
Assess relevant deviation for subjects who are randomised. Assess the open-label and double-blind treatment periods together. Exclusion would start from the 14th consecutive day that the medication is <math>< 1500</math>mg per day or adjusted from their maximal tolerated dose

IPD code	IPD Category	Explanation	PP Relevant IPD	Exclusion level

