4.3	Saxagliptin treatment non-compliance	Randomized subjects who took no dose of saxagliptin for $\geq 2$ consecutive weeks of the days in the open-label or double-blind period	8. Randomized subjects who took no dose of saxagliptin for $\geq 2$ consecutive weeks of the days in the open-label or double-blind period	Partially exclude from PP analysis set (if occurs during double blind) Completely exclude from PP analysis set (if occurs during open label) Assess relevant deviation for subjects who are randomised. Assess the open-label and double-blind treatment periods together. Exclusion would start from the 14th consecutive day that saxagliptin was stopped.
4.4	Deviation of rescue treatment procedure	Subjects did not receive open label rescue medications when met rescue criteria		

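### SAP deviation item 4.1a omits the protocol's exemption for allowed rescue medication, so, read literally, subjects rescued as the protocol requires are recorded as prohibited-medication deviations

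*SAP*

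**What the plan says.** Protocol 3.8.1 lists what enrolled subjects may not take: "Antihyperglycemic medication (other than protocol required medication and/or protocol-allowed open-label rescue medication". That names two separate exceptions.

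SAP Appendix 1, item 4.1a, is the matching entry in the list of important protocol deviations (IPDs). It covers "Randomised subjects who used anti-hyperglycemic therapy (other than protocol required medications) for ≥14 consecutive days during the" open-label or double-blind period. The same text is PP-relevant deviation 5. Use during the double-blind period leads to partial exclusion from the PP set: "Exclusion would start from the 14th consecutive day that the medication is taken".

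Three other rules bear on this item:

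- Protocol 4.3, below Table 2: "If the repeat central laboratory FPG value still meets the criterion, the subject must be rescued". It adds: "Rescued subjects will then continue in the double-blind treatment period according to their original visit schedule".
- SAP Appendix 1, item 4.4, makes the opposite conduct an important deviation: "Subjects did not receive open label rescue medications when met rescue criteria".
- Protocol 3.9.3, for subjects who stop investigational product (IP) and stay on the visit schedule: "Medication for the management of subject's diabetes would be under care and direction of the investigator".

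SAP 4.2.1 summarises important deviations by treatment for the ITT set and lists them. After early termination, SAP Section 4.4 expressly keeps the listing.

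**The concern.** The deviation list follows Protocol 3.8.1 but loses half of its exception. A site that confirms the fasting plasma glucose (FPG) criterion and starts rescue does what the protocol demands. Once that rescue has run for 14 days, the subject meets the wording of a deviation headed as prohibited medication. Had the site not rescued, item 4.4 would apply instead. SAP 2.2 says the deviation report draws partly on programmed checks, and a program applies the wording it is given.

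At stake is how the deviation table or listing reads. Rescue is an outcome of randomised treatment. A reader who sees more prohibited-medication deviations on placebo would take it as poor conduct, when it reflects lack of glycaemic control handled correctly. The PP-relevant flag would also be attached to subjects who did not depart from the protocol.

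A second, smaller gap concerns treatment after IP stops. It is neither required medication nor rescue, and item 4.1a says nothing about it.

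**Working it through.** **1. The plan's own figures.** With 108 per arm, a difference of 0.5 and an SD of 1.0, power = Φ(0.5/√(2/108) − 1.96) = Φ(3.674 − 1.960) = 0.957, against 95% stated. Allowing for 5% without a post-baseline value, 108/0.95 = 113.7, so 114 per arm and 3 × 114 = 342. Both reproduce and are not in dispute. The per-arm split is about 91 in China and 23 elsewhere.

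**2. The texts side by side.**

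| Situation | Protocol | SAP Appendix 1, read literally |
|---|---|---|
| Criterion confirmed, rescue given for 14 days or more | Required (4.3), exempt from the ban (3.8.1) | Deviation under 4.1a, PP-relevant 5 |
| Criterion confirmed, rescue given for under 14 days | Same | No deviation under 4.1a |
| Criterion confirmed, no rescue | Not permitted (4.3) | Deviation under item 4.4 |
| IP stopped, diabetes treated by the investigator for 14 days or more | Permitted (3.9.3) | Caught by 4.1a if the double-blind period is taken to run on after IP stops; the SAP does not say |

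**3. Would rescue usually last 14 days?** Take the latest routine trigger, the Week 18 visit. Its target is day 127 (SAP Table 1) and its window ±5 days (Protocol Table 1). The repeat visit falls up to 5 days after the first result. Let *t* be the central-laboratory turnaround per sample, which the documents do not give, and assume rescue starts when the repeat result arrives.

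- Start of rescue = 127 + 5 + *t* + 5 + *t* = 137 + 2*t*.
- Days on rescue by day 169 (Week 24) = 169 − (137 + 2*t*) + 1 = 33 − 2*t*.
- Days on rescue by day 164 (early edge of the Week 24 window) = 28 − 2*t*.

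| *t* (days, assumed) | Start day | Days by 169 | Days by 164 |
|---|---|---|---|
| 1 | 139 | 31 | 26 |
| 7 | 151 | 19 | 14 |
| 10 | 157 | 13 | 8 |

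For turnaround of up to a week, even the latest routine rescue reaches the threshold if it is continued. At *t* = 7 with an early Week 24 visit it only just does.

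**4. How many subjects?** SAP Section 4.4 says the study closes without recruiting in China, so the relevant planning figure is about 23 per arm; the number actually randomised is not given. The rescue rates below are assumptions.

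- Placebo: 23 × 5% = 1.2 and 23 × 20% = 4.6, so about 1 to 5.
- Each dapagliflozin arm: 23 × 1% = 0.2 and 23 × 5% = 1.2, so about 0 to 1.

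The direction is an inference. Rescue is triggered by FPG, and the earlier add-on study cited in Protocol 1.1 reports FPG changes of −32.7 mg/dL with dapagliflozin and −5.3 mg/dL with placebo. Equal rescue rates would give no imbalance.

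**5. Does the PP estimate move?** The PP analysis is an MMRM similar to the primary one (SAP 4.2.4.2, Sensitivity analysis). The primary analysis already drops values recorded after rescue and values more than 8 days after the last dose. For double-blind use, deviation 5 cuts data only from the 14th day of treatment. For a rescued subject that cut comes after the existing one and should remove no further HbA1c value.

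**The case against.** The best defence is that rescue is exempt by implication. SAP 2.2 defines important deviations as a subset of protocol deviations, and rescue given as directed is not one. Protocol 4.3 makes rescue mandatory, Protocol 7.2 lists rescue therapy among the study medications, and item 4.4 treats it as required. A sensible person applying the list by hand might well leave rescued subjects out. That stands as an account of what was probably meant. It does not cure the text: Protocol 3.8.1 names rescue separately from required medication, and the SAP repeats only the latter term. At best the row is ambiguous, which is not good enough for a programmed check.

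The defence is right about consequences. A reader might infer that rescued placebo subjects drop out of the PP set and so shrink the treatment difference. The documents do not support that. SAP 2.2 refers to Appendix 1 for the action to be taken, and Appendix 1 prescribes partial exclusion for double-blind use. Post-rescue values are already gone from the model.

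A reader might also infer that post-IP treatment adds to an imbalance against placebo. No direction can be derived: Protocol 3.9.1 lists adverse events, reduced eGFR, hypersensitivity and subject decision among the reasons for stopping. Those subjects may in any case be flagged under PP-relevant deviation 13, for IP not taken for two weeks or more.

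Finally, SAP Section 6 cancels everything outside Section 4.4, so no PP efficacy analysis remains and the practical reach is small.

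**Conclusion.** The point holds as a defect in deviation classification. Item 4.1a and PP-relevant deviation 5 do not carry the rescue exemption of Protocol 3.8.1. With item 4.4 beside them, a subject who meets rescue criteria is a deviation if not rescued and, as written, also a deviation once rescued for 14 days or more. It would go too far to say that everyone meeting the criteria is flagged either way, since shorter rescue escapes item 4.1a.

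The effect falls on the by-arm deviation summary in the full plan, the listing kept after early termination, and the PP-relevant flags. Sample size, power, type I error and the primary analysis are untouched, and the PP HbA1c estimate should be essentially unchanged. On about 23 subjects per arm the likely size is 1 to 5 mislabelled placebo subjects and 0 to 1 per dapagliflozin arm. That rests on the assumed rescue rates and on rescue continuing for at least 14 days. Counting on the full 114 per arm would overstate it, given closure without recruitment in China.

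For treatment after IP stops, the finding is only that the item is silent where Protocol 3.9.3 says such medication "would be under care and direction of the investigator". No arm imbalance is claimed there.

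**What to change.** In item 4.1a and PP-relevant deviation 5, extend the bracketed exception to read: *other than protocol required medications and protocol-allowed open-label rescue medication*. This matches Protocol 3.8.1. Update the programmed check accordingly.

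In the same row, reconcile the item with Protocol 3.9.3, so that diabetes treatment given after permanent discontinuation of IP is not labelled prohibited. State whether the double-blind period, for this item, ends when IP stops. PP-relevant deviation 13 may still apply to those subjects and can stay as it is.

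The cost is one appendix row and its programmed check. No new data are needed and no clinical rule changes. SAP 2.2 has the list finalised before unblinding, so the correction belongs before that point.

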## 2. Target Population

### a. For inclusion into open-label treatment period of Stratum A

Subjects with T2DM with inadequate glycaemic control, defined as central laboratory HbA1c  $\geq 8.0\%$  and  $\leq 11.5\%$  obtained at the screening visit (i.e., Week -18), on stable metformin therapy alone at a dose  $\geq 1500$  mg per day or a maximal tolerated dose for at least 8 weeks prior to screening visit

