### **7.7.2 Metformin**

Up to Week 24, subjects should continue to administer the same type and dose of metformin therapy they were using at study entry. Metformin should be administered and stored according to product and country-specific labelling.

Metformin will not be provided by the Sponsor.

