#### **4.2.2.2 Other baseline characteristics**

Standard descriptive statistics will be presented for the continuous variables of:

- Duration of Type 2 Diabetes (years).
- HbA1c
- FPG
- PPG
- Estimate glomerular filtration rate (eGFR, Modification of Diet in Renal Disease (MDRD))

The total frequency counts and percentages of subjects will be presented for the categorical variables of:

- Randomisation stratification factors (Stratum A, Stratum B)
- HbA1c (grouped as: <8.0%, 8.0% to <9.0%,  $\geq$ 9.0%)
- Duration of Type 2 Diabetes (years) (grouped as < 3,  $\geq$  3 and  $\leq$  10, > 10)
- eGFR (mL/min/1.73m^2) (grouped as <30,  $\geq$ 30 and <60,  $\geq$ 60 and <90,  $\geq$ 90)
- Metformin dose (mg) (group as: <1500,  $\geq$  1500 and <1701,  $\geq$ 1701 and <2500,  $\geq$ 2500)

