### **4.4 Early termination analyses**

On Jun 30, 2020 AstraZeneca decided to stop commercialization of QTERNMet/Qtrilmel and to withdraw all active licenses, for business reasons. DS-NAVIGATION will be closed without recruiting subjects in China and patients recruited from Thailand and Vietnam will complete the study.

Therefore, the planned analyses in this study will be conducted over all data available. To support the synopsis format CSR, the following analysis will be performed:

- Summaries of subject disposition, summaries in the Enrolled subjects set and Open-label treated subjects analysis set, as described in Section 4.2.1. Subject disposition will also be listed.
- Summary of analysis set, defined in Section 2.1.
- Demographic and baseline characteristics as described in Section 4.2.2 and Section 4.2.2.1.
- An overall summary of adverse events at subject level, including TEAEs, TESAEs, death, hypoglycaemia, severe events, treatment-related events, events leading to the discontinuation of study medication, events leading to death will be presented for open-label treatment period and double-blind treatment period. TEAEs will also be summarised by SOC and PT in open-label and double-blind treatment. TESAEs will be summarised by SOC and PT in the double-blind period only. AEs and SAEs will also be listed.
- Important protocol deviations, observed HbA1c data, and marked abnormalities by test will be listed.

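### Read as written, SAP deviation item 4.2 removes compliant subjects on a maximal tolerated metformin dose below 1500 mg/day from the per-protocol set and misses forbidden changes from a non-maximal entry dose that stay at or above 1500 mg/day

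*SAP*

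**What the plan says.** **Entry.** Protocol 3.1, criterion 2a (Stratum A) accepts stable metformin of at least 1500 mg/day "or a maximal tolerated dose for at least 8 weeks prior to screening visit". Criterion 2b (Stratum B) offers the same alternative. A tolerated dose below 1500 mg/day is therefore eligible.

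**During the study.** Protocol 7.7.2 says that up to Week 24 "subjects should continue to administer the same type and dose of metformin therapy they were using at study entry". The text under Table 2 in Protocol 4.3 adds: "Adjustment of study medication (includes metformin) will not be allowed at any time during the study". Neither sentence depends on the dose level or on the direction of a change.

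**Deviation rule.** SAP Appendix 1, item 4.2, carries the category of adjustment of background medication. It flags "Randomised subjects who took metformin $< 1500$ mg per day or adjusted from their maximal tolerated dose" for at least two consecutive weeks after enrolment, and the PP-relevant column repeats this as number 7. The exclusion is partial if the deviation occurs in the double-blind period. For the open-label period the entry reads "Completely exclude from PP analysis set (if occurs during open label". On timing it says "Exclusion would start from the 14th consecutive day that the medication is" below 1500 mg per day or adjusted from the maximal tolerated dose.

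**Use of the PP set.** It supports the third HbA1c sensitivity analysis (SAP 4.2.4.2) and a repeat of the demographic and baseline tables (SAP 4.2.2). After early termination, SAP 6 limits the work to SAP 4.4. That section keeps the summary of analysis sets and the baseline tables and states: "Important protocol deviations, observed HbA1c data, and marked abnormalities by test will be listed".

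**The concern.** The trial asks what dapagliflozin adds to an unchanged background of metformin and saxagliptin. A per-protocol check of that background should keep subjects who held their entry dose and set aside those who did not. Item 4.2 instead tests the dose against a fixed 1500 mg/day threshold, and tests for change only in subjects at their maximal tolerated dose.

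This can go wrong in both directions. Some subjects who followed the protocol exactly would be listed as important deviators and lost from the PP set. Some whose background therapy changed for weeks would stay in it with nothing recorded under this item. The PP analysis would then be a poorer robustness check than intended, and the deviation listing would misstate who deviated.

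**Working it through.** **1. Put the rule and the protocol side by side.** The doses below are illustrations, not figures from the documents. Item 4.2 is read literally: flag if the duration is at least 14 days and either the dose is below 1500 mg/day or it was changed from the maximal tolerated dose (MTD). The protocol's test is simply whether the dose differs from the entry dose. Open-label treatment lasts 16 weeks (112 days) in Stratum A and 8 weeks (56 days) in Stratum B; both exceed 14 days.

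| Case | Flagged by item 4.2? | Changed from entry dose? |
|---|---|---|
| MTD 1000 mg, unchanged, Stratum A (112 days) | Yes | No |
| MTD 1000 mg, unchanged, Stratum B (56 days) | Yes | No |
| 2000 to 1500 mg, entry dose not the MTD, at least 2 weeks | No | Yes |
| 1500 to 2500 mg, entry dose not the MTD, at least 2 weeks | No | Yes |
| 2000 mg that is the MTD, cut to 1500 mg, at least 2 weeks | Yes | Yes |
| 2000 to 1000 mg, at least 2 weeks | Yes | Yes |
| 2000 to 1000 mg, 10 days | No | Yes |
| 2000 mg, unchanged | No | No |

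Rows 1 and 2 are wrong flags. Because the condition is met during open-label treatment, they lead to complete exclusion. Rows 3 and 4 are misses. Row 5 shows that a change at or above 1500 mg/day is caught when the entry dose was the MTD. Row 7 is missed only because of the two-week threshold, which is a reasonable choice of what counts as important.

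**2. Check whether another item covers rows 3 and 4.**
- Item 1.2 (PP-relevant 2) looks at stability only as of the start of open-label treatment.
- Item 4.1 (PP-relevant 5) concerns glucose-lowering drugs other than those the protocol requires; metformin is required.
- Item 5.1 (PP-relevant 9) mentions incorrect study medication or dosing, but stands under the investigational product heading and concerns dispensed kits. Protocol 7.1 lists metformin as a non-investigational product.
- Item 8.3 is a discretionary category with no PP rule.

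None clearly covers them. By contrast, the exclusion note for systemic glucocorticoids in item 4.1 counts titration in either direction.

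**3. Size.** The plan's own counts reproduce: 108 / 0.95 = 113.7, so 114 per arm, and 3 x 114 = 342. Of each 114, about 91 were planned from China and about 23 from elsewhere. SAP 4.4 says the trial closes without recruiting in China, so the relevant planned number is 3 x 23 = 69. The share on a tolerated dose below 1500 mg/day is not given. As assumptions:
- 5%: 69 x 0.05 = 3.45, about 3
- 10%: 69 x 0.10 = 6.9, about 7
- 15%: 69 x 0.15 = 10.35, about 10

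The number of missed changes cannot be derived.

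**4. Effect on the PP analysis as originally planned.** Nominal power is Phi(0.5 / (1.0 x sqrt(2/n)) - 1.96). With n = 108 per group this is Phi(3.674 - 1.96) = 0.957, against the stated 95%. Losing 5% leaves 103 per group and 94.8%; losing 10% leaves 97 and 93.6%. Loss of precision would have been small; the issue is who is in the set.

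**The case against.** **Intent.** The strongest defence is that item 4.2 means something narrower than it says. SAP 2.2 defines important deviations as a subset of protocol deviations, and a subject on an unchanged, eligible tolerated dose has no deviation. The row's category is adjustment, and its two limbs mirror the two entry routes. This makes it likely that subjects at their maximal tolerated dose were meant to be judged only on change. It does not cure the text: the limbs are joined by *or*, there is no exemption, and the same wording recurs across the row's columns. Someone programming the row as written would exclude these subjects. A reader might infer that the SAP deliberately discards compliant subjects; the documents do not support that.

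**Changes at or above 1500 mg/day.** A reader might infer that all such changes escape. They do not: a change of at least two weeks from a maximal tolerated dose is flagged at any dose level. It is also fair that not every forbidden change need be an important deviation. But item 4.2 already treats two weeks of altered metformin as important in some subjects, and gives no reason to treat others differently.

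**The baseline category.** SAP 4.2.2.2 lists "Metformin dose (mg) (group as: <1500" as a group, which might be read as proof that such subjects are expected. This is weak evidence: the same list has eGFR groups below 60, although Protocol 3.2 excludes those subjects. Eligibility rests on criteria 2a and 2b alone.

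**Correction later.** SAP 2.2 says the list is finalised before unblinding, and Protocol 8.3.1 sets the PP criteria after deviation review. This leaves room to correct the row, but neither passage corrects it.

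**Conclusion.** The concern holds in both parts, each within limits. Item 4.2 as written (a) flags, and completely excludes from the PP set, subjects who kept an eligible maximal tolerated dose below 1500 mg/day, and (b) does not flag changes of at least two weeks from a non-maximal entry dose when the new dose stays at or above 1500 mg/day.

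The consequences are modest. The primary analysis uses the ITT set and is untouched. The third HbA1c sensitivity analysis would have been affected, but under SAP 6 it is no longer run. What remains exposed is the analysis-set summary, the PP repeat of the baseline tables and the listing of important deviations.

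The figure of about 3 to 10 wrongly flagged subjects rests on two assumptions: a 5% to 15% share below 1500 mg/day, and 69 randomised subjects as planned outside China. Two larger claims are tempting. Applying the same shares to 342 gives about 17 to 51, but that total includes Chinese subjects who will not be recruited. And metformin increases in poorly controlled placebo subjects could in principle narrow the PP difference, but nothing in the documents shows that this happened, and Protocol 7.7 requires changes in concomitant regimens to be reported to the sponsor.

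**What to change.** Reconcile item 4.2 and PP-relevant deviation 7 with the protocol's own entry and no-change rules:

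- **Change limb.** Flag randomised subjects whose daily metformin dose differed, up or down, from their study-entry dose for at least two consecutive weeks after enrolment. Start the exclusion at the 14th consecutive day on the changed dose, and keep the row's present distinction between open-label and double-blind periods.
- **Below-1500 mg limb.** Apply it only to subjects whose entry dose was not a documented maximal tolerated dose. Dropping the limb altogether would lose a check on subjects entered below 1500 mg/day without being at their maximal tolerated dose, because item 1.2 is worded around stability.
- **Description.** Keep the count of subjects ever below 1500 mg/day in SAP 4.2.3.3 as a summary only.

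This takes no view on metformin dosing; it makes the analysis rule follow what the protocol already states. The cost is one appendix row and one programmed check. SAP 4.2.2.2 and 4.2.3.3 already need the dose data. Maximal-tolerated-dose status is already needed for the second limb of the present rule, although the documents do not say how it is recorded; that should be confirmed before the list is finalised.
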